- b Note: A “clinically meaningful” response is a PASI 75 response, which represents at least a 75% decrease (improvement) from the baseline PASI score. A “high level” of clinical response is a PASI 90 response, which represents at least a 90% decrease (improvement) from baseline in PASI score, or sPGA (0,1) response, which represents an “almost clear” response. The “highest level” of clinical response is a PASI 100 or sPGA (0) response, which represents complete resolution of psoriasis.

Summary of Study Design:

Study AMAK is a Phase 3, multicenter, randomized, double-blind, placebo-controlled, parallel-group, multi-period study. The study design includes 2 treatment periods (Induction and Maintenance with Randomized Withdrawal), which together last for up to 52 weeks, followed by a 12-week Post-Treatment Follow-Up period. The study population consists of patients aged 18 years or older at the time of screening who have chronic plaque psoriasis based on a

confirmed diagnosis of chronic plaque psoriasis for at least 6 months, are candidates for systemic and/or phototherapy, and have $\geq 10\%$ body surface area (BSA) involvement, a static Physician's Global Assessment (sPGA) score of ≥ 3 , and a Psoriasis Area and Severity Index (PASI) score ≥ 12 at screening and at baseline.

Treatment Arms and Duration:

Patients will be randomized 4:1 to receive double-blind ("blinded") subcutaneous (SC) administration of 250 mg mirikizumab or matching placebo at Weeks 0, 4, 8, and 12. Randomization will be stratified based on previous exposure to biologic therapy (yes/no), body weight (< 100 kg or ≥ 100 kg), and geographic region (North America or Other). Patients who were responders (\geq PASI 90) in the Induction Period and who continue in the blinded Maintenance Period will be monitored for maintenance of response or remission, as well as relapse and disease rebound following treatment withdrawal, and response to retreatment following relapse. Responders to mirikizumab treatment in the blinded Induction Period will be re-randomized 1:1:1 to 250 mg mirikizumab every 8 weeks (Q8W), 125 mg mirikizumab Q8W, or placebo Q8W, with treatments beginning at Week 16. Stratification in the Maintenance Period will be by body weight at baseline (< 100 kg or ≥ 100 kg). The duration of treatment is 52 weeks. The total duration of participation in this study may be up to 68 weeks as detailed below.

Screening Period: Up to 4 weeks.

Treatment Period: Approximately 52 weeks.

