Abbreviations: BP = blood pressure; BSA = body surface area; conc = concentration; C-SSRS = Columbia–Suicide Severity Rating Scale; DLQI = Dermatology Life Quality Index; DNA = deoxyribonucleic acid; ECG = electrocardiogram; EQ-5D-5L-PSO = European Quality of Life–5 Dimensions–5 Levels–Psoriasis; ETV = early termination visit; FSH = follicle stimulating hormone; HBcAb = anti-hepatitis B core antibody; HBsAb = hepatitis B surface antibody; HBsAg = hepatitis B surface antigen; HBV = hepatitis B virus; HCV = hepatitis C virus; HIV = human immunodeficiency virus; hsCRP = high-sensitivity C-reactive protein; IL-19 = interleukin-19; IP = investigational product; LV = last study visit; miri = mirikizumab; NAPSI = Nail Psoriasis Severity Index; PASI = Psoriasis Area and Severity Index; PatGA = Patient’s Global Assessment of Psoriasis; PK = pharmacokinetic; PPASI = Palmoplantar Psoriasis Severity Index; PPD = purified protein derivative (skin test); PSS = Psoriasis Symptoms Scale; PSSI = Psoriasis Scalp Severity Index; QIDS-SR16 = 16-item Quick Inventory of Depressive Symptomatology; RNA = ribonucleic acid; SF-36 = Medical Outcomes Study 36-Item Short Form Health Survey; sPGA = static Physician’s Global Assessment; Suppl. = supplement; TB = tuberculosis; temp = temperature; TSQM = Treatment Satisfaction Questionnaire for Medication; V = visit; W = weeks; WCBP = women of childbearing potential; WPAI-PSO = Work Productivity and Activity Impairment Questionnaire: Psoriasis.

- a All activities should be completed prior to any study dose administration, unless otherwise stated.
- b Visit 1 procedures may be conducted over more than 1 day, as long as all tasks are completed within the allowable visit tolerance (at least 3 days should be allowed for receipt of laboratory test results).
- c One complete physical examination (excluding pelvic or rectal examinations) to include heart, lungs, peripheral lymph nodes, and abdomen, and visual examination of all skin areas (including genitalia and breast areas) will be performed at screening. All physical examinations throughout the study should include a symptom-directed evaluation as well as examination of heart, lungs, peripheral lymph nodes, and abdomen, and visual examination of all skin areas (including genitalia and breast areas).

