- d Sitting blood pressure, temperature, and pulse will be obtained within approximately the same time frame as ECG measurements or blood sampling. When multiple assessments are scheduled for the same time point, the preferred order of completion should be as follows: ECG (if applicable), vital signs, and then blood sampling.
- e Chest radiography will be performed locally at screening unless it has been performed within 3 months before initial screening (provided the radiographs and/or formal report are available for the investigator’s review). For additional details, see Section 9.4.5.3.
- f TB testing will be performed at screening unless it has been performed within 3 months before initial screening (provided the formal report is available for the investigator’s review). It may also be performed after screening if clinically indicated. TB testing will be performed locally using an interferon- γ release assay (IGRA; QuantiFERON[®]-TB Gold or T-SPOT.TB[®]) or a purified protein derivative (PPD) tuberculin skin test. If PPD test is performed, patients will return 2 to 3 days afterwards to have their PPD test read. For additional details on TB testing, see Exclusion Criterion [19] and Section 9.4.5.2.
- g The preferred order of completion is supine ECG prior to vital signs, blood sampling, or any other study procedures. For additional details on ECG collection, see Section 9.4.1. ECG should be performed at the ETV and Visit 802 only if there is early termination due to a cardiovascular event.
- h A Self-Harm Follow-Up Form is to be completed only during visits for which there is at least 1 discrete self-harm event identified on the Self-Harm Supplement Form (see Section 9.2.2).
- i PSSI, NAPSI, and PPASI assessments are applicable only if symptoms are present at baseline.
- j These assessments should be completed before administration of investigational product, before the patient’s clinical examination, before the patient receives any tests or results, and before the patient’s health, health data, or emotions are discussed.
- k Electronic diaries will be distributed at the screening visit and collected at the Week 16 visit.
- l Unscheduled hematology or blood chemistry panels may be performed at the discretion of the investigator.
- m Patients should not eat or drink anything except water for 12 hours prior to sample collection.

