5.1.1. Screening Period

Patients will be evaluated for study eligibility ≤ 28 days before the baseline visit (Visit 2). The patient will sign the informed consent form (ICF) prior to any study assessments, examinations, or procedures being performed. Screening procedures will be performed according to the Schedule of Activities (Section 2). Electronic diary collection will begin at screening, approximately ≤ 28 days prior to Visit 2 (baseline). All inclusion and exclusion criteria are provided in Sections 6.1 and 6.2, respectively.

5.1.2. Baseline and Double-Blind Induction Period (Week 0 to Week 16):

At Visit 2 (Week 0; baseline), patients who meet the study eligibility criteria will be randomized 4:1 to receive 250 mg mirikizumab or matching placebo (SC), respectively, at Weeks 0, 4, 8, and 12. Randomization will be stratified, based on previous exposure to biologic therapy (yes/no), body weight (< 100 kg or ≥ 100 kg), and geographic region (North America or Other).

Patients who discontinue the study for any reason during this period will stop treatment and continue to the early termination visit (ETV) and then complete the 12-week Post-Treatment Follow-up Period.

5.1.3. Double-Blind Maintenance Period (Week 16 to Week 52 [36 Weeks]):

All patients who complete the Induction Period may continue in the Maintenance Period.

The Maintenance Dosing Period will be a double-blind treatment period with randomized withdrawal. The first injection of study drug for this period will be at Week 16, with the last injection at Week 48.

At Week 16 (Visit 7), patients who enter the Maintenance Period will be classified as a responder (\geq PASI 90) or non-responder ($<$ PASI 90). Patients who are responders at Week 16 will be monitored for maintenance of response or remission, as well as relapse and disease rebound following treatment withdrawal, and response to retreatment following relapse.

Remission is defined as the achievement of PASI 100. **Relapse** is defined as the loss, at any

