6.1.3. Definition of Study Baseline

For efficacy and health outcomes, study baseline is defined as the last non-missing assessment (including unscheduled visits) before the first injection, which in most cases will be the measure recorded at Week 0 (Visit 2). For efficacy/health outcome measures, if the patient does not take any injection, the last available value on or prior to the randomization date will be used. In cases where baseline measurements are taken on the same day as the injection, the baseline measurements are used as the baseline for data analysis.

For the Psoriasis Symptom Scale (PSS), the weekly average of at least 4 days of the consecutive 7 days prior to the first injection (or randomization, if the patient does not take any injection) will be the study baseline score.

Baseline for safety analysis is described in the Safety section (Section 6.13).

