6.5. Multiple Comparisons/Multiplicity

A prespecified graphical multiple testing approach (Bretz et al. 2009, 2011) will be implemented to control the overall Type I error rate at 2-sided alpha of 0.05, for all primary and major secondary endpoints. More specifically, we will calculate multiple testing adjusted p-values using “Algorithm 2” described by Bretz et al. (2009), and any hypothesis tests with a multiple testing adjusted p-value of less than 0.05 will be considered statistically significant. This graphical approach is a closed testing procedure; hence, it strongly controls the family-wise error rate across all endpoints (Bretz et al. 2009, 2011; Alosh et al. 2014). Each hypothesis is represented as a node in a graph. Directed arrows between the nodes with associated weights represent how alpha is passed from its initial allocation to other nodes. The testing scheme will be fully specified by the graph (including nodes, arrows, and weights) along with the initial alpha allocation. [Figure AMAK.6.1](#) describes the graphical scheme, and all of our alphas will be allocated to the sPGA (0,1) endpoint initially. The testing scheme will be finalized before the first unblinding of efficacy data.

Abbreviations: BSA = body surface area; DLQI = Dermatology Life Quality Index; miri = mirikizumab; PASI = Psoriasis Area and Severity Index; PASI 75/90/100 = $\geq 75\%$ / $\geq 90\%$ / $= 100\%$ improvement in PASI from baseline; PBO = placebo; PSS = Psoriasis Symptoms Scale; Q8W = every 8 weeks; sPGA = static Physician’s Global Assessment; vs. = versus; W = Week.

- ^a PSS Symptom Free at Week 16 is performed for patients with study baseline PSS symptom score ≥ 1 in Induction ITT population.
- ^b DLQI (0,1) and reduction in DLQI ≥ 5 at Week 16 is performed for patients with study baseline DLQI ≥ 5 in Induction ITT population.
- ^c Re-randomized Maintenance ITT population.

Figure AMAK.6.1. Graphical approach to control type 1 error rate for Study AMAK.

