Appendix 1. Study Visit Definition for Psoriasis Symptoms Scale (PSS)

Psoriasis Symptoms Scale (PSS) is collected as a daily diary, entries will be mapped to study week by the following:

Week^a	Start Day^b	End Day
Baseline	Date of First Injection -7	Date of First Injection-1
Week 1	Max (Baseline Assessment Date, Week 2 Assessment Date – 14)	Week 2 Assessment Date - 8
Week 2	Max (Baseline Assessment Date, Week 2 Assessment Date – 7)	Week 2 Assessment Date - 1
Week 3	Max (Week 2 Assessment Date, Week 4 Assessment Date – 14)	Week 4 Assessment Date -8
Week 4	Max (Week 2 Assessment Date, Week 4 Assessment Date – 7)	Week 4 Assessment Date – 1
Week 5	Max (Week 4 Assessment Date, Week 8 Assessment Date – 28)	Week 8 Assessment Date -22
Week 6	Max (Week 4 Assessment Date, Week 8 Assessment Date – 21)	Week 8 Assessment Date -15
Week 7	Max (Week 4 Assessment Date, Week 8 Assessment Date – 14)	Week 8 Assessment Date -8
Week 8	Max (Week 4 Assessment Date, Week 8 Assessment Date – 7)	Week 8 Assessment Date – 1
Week 9	Max (Week 8 Assessment Date, Week 12 Assessment Date – 28)	Week 12 Assessment Date -22
Week 10	Max (Week 8 Assessment Date, Week 12 Assessment Date – 21)	Week 12 Assessment Date -15
Week 11	Max (Week 8 Assessment Date, Week 12 Assessment Date – 14)	Week 12 Assessment Date -8
Week 12	Max (Week 8 Assessment Date, Week 12 Assessment Date – 7)	Week 12 Assessment Date – 1
Week 13	Max (Week 12 Assessment Date, Week 16 Assessment Date – 28)	Week 16 Assessment Date -22
Week 14	Max (Week 12 Assessment Date, Week 16 Assessment Date – 21)	Week 16 Assessment Date -15
Week 15	Max (Week 12 Assessment Date, Week 16 Assessment Date – 14)	Week 16 Assessment Date -8
Week 16	Max (Week 12 Assessment Date, Week 16 Assessment Date – 7)	Week 16 Assessment Date – 1

Abbreviation: Max = maximum.

^a If End Day < Start Day, do not assign specified visit week.

^b Assessment Date is the date of the specified visit week's PASI assessment.

If multiple PSS assessments on a single day are present, use the latest assessment. If more than 7 days are available between assessment dates, use only the last 7 days as the range. If the range contains at least 4 nonmissing daily assessments, calculate the average for the nonmissing daily assessments to get the weekly score. If range contains fewer than 4 nonmissing daily assessments, then the weekly result is missing.

Leo Document ID = f4582dcd-ecee-4563-926b-d744d4903f79

Approver: PPD
Approval Date & Time: 28-Mar-2019 19:37:34 GMT

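### The protocol sets no minimum diary lead time before first dose, so a permitted 3-day screening makes the PSS baseline of a major secondary endpoint impossible

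*Protocol*

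**What the plan says.** **Screening length.** The Protocol synopsis gives a ceiling: "Screening Period: Up to 4 weeks". Section 5.1.1 and the Schedule of Activities put it at no more than 28 days before Visit 2. The only lower figure is in Schedule footnote b, which lets Visit 1 procedures run over more than one day and adds that "at least 3 days should be allowed for receipt of laboratory test results".

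**Diary.** Section 5.1.1 says "Electronic diary collection will begin at screening", and Schedule footnote k says "Electronic diaries will be distributed at the screening visit and collected at the Week 16 visit". The Schedule shows the PSS only as a daily diary up to Week 16. No separate office PSS is marked at Visit 2.

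**PSS baseline.** SAP 6.1.3 gives the PSS its own rule, apart from the general last-non-missing rule: "the weekly average of at least 4 days of the consecutive 7 days prior to the first injection". SAP Appendix 1 starts the window at "Date of First Injection -7" and ends it the day before the injection. It adds: "If range contains fewer than 4 nonmissing daily assessments, then the weekly result is missing". No fallback is given.

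**Use of the baseline.** A PSS symptoms score of 0 at Week 16 is a major secondary endpoint in the graphical testing procedure. The footnote to Figure AMAK.6.1 in SAP 6.5 restricts it: "PSS Symptom Free at Week 16 is performed for patients with study baseline PSS symptom score" of at least 1.

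**The concern.** The two rules were written separately and do not meet. One lets the first dose follow Visit 1 after about 3 days. The other needs 4 completed diary days before that dose, and the diary does not exist before Visit 1.

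A patient who falls into this gap has no PSS baseline, and none can be collected after the first injection. That patient cannot be shown to have a baseline symptoms score of at least 1, and so falls out of the Week 16 PSS endpoint. SAP Table AMAK.6.5 also makes every PSS change from baseline missing when the baseline is missing.

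Nothing in the plan catches this. Inclusion criterion [6] asks that patients be able and willing to use the electronic device, but sets no number of completed diary days. Non-responder imputation (SAP 6.3.1) covers missing response data at the analysis time point and does not mention a missing baseline.

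**Working it through.** **The plan's own figures.** Neither document gives power, response rates or an evaluable number for the PSS endpoint. The stated power above 95% for the primary endpoints reproduces: with 400 against 100 patients and two-sided alpha 0.05, 70% vs 5% (sPGA 0,1) and 70% vs 3% (PASI 90) both give more than 99.9%. Those endpoints do not use the diary and are untouched here.

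**Step 1: possible diary days.** Let *k* be the number of days from diary issue to first injection. The window is Day -7 to Day -1, so the possible entries *m* are:
- first entry on the day of issue: m = min(k, 7)
- first entry the next day: m = min(k - 1, 7)

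At k = 3, m is 3 or 2, below the required 4. At k = 4, m is 4 or 3. With perfect completion a baseline therefore needs k of at least 4 (same-day start) or 5 (next-day start).

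**Step 2: how fragile the baseline is.** With daily completion probability *p* and independent days (both assumptions), the chance of a usable baseline is P(X ≥ 4), where X is binomial(m, p). For example, m = 5 and p = 0.8 gives 0.8⁵ + 5 × 0.8⁴ × 0.2 = 0.328 + 0.410 = 0.737.

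| k (days) | same-day start, p = 0.9 | same-day start, p = 0.8 | next-day start, p = 0.8 |
|---|---|---|---|
| 3 | 0 | 0 | 0 |
| 4 | 0.66 | 0.41 | 0 |
| 5 | 0.92 | 0.74 | 0.41 |
| 6 | 0.98 | 0.90 | 0.74 |
| 7 | 0.997 | 0.97 | 0.90 |
| 8 or more | 0.997 | 0.97 | 0.97 |

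**Step 3: what lost patients would cost.** The PSS response rates, the alpha and the fraction lost below are all assumptions. Figure AMAK.6.1 is not reproduced in the text available, so the alpha reaching this hypothesis is unknown. The approximation is

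power = Φ[(d - z × SE₀) / SE₁],

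where d is the difference in proportions, SE₀ uses the pooled proportion and SE₁ the separate ones.

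For 10% vs 1% with 400 and 100 patients:
- pooled proportion = (40 + 1)/500 = 0.082
- SE₀ = √(0.082 × 0.918 × 0.0125) = 0.0307
- SE₁ = √(0.01 × 0.99/100 + 0.10 × 0.90/400) = 0.0180
- power at alpha 0.05 = Φ[(0.09 - 1.96 × 0.0307)/0.0180] = Φ(1.66) = 0.952

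| Assumed rates, alpha | none lost | 10% lost | 20% lost | 30% lost |
|---|---|---|---|---|
| 20% vs 2%, 0.05 | >99.9% | >99.9% | 99.9% | 99.8% |
| 10% vs 1%, 0.05 | 95.2% | 92.0% | 87.1% | 80.0% |
| 10% vs 1%, 0.025 | 88.1% | 82.2% | 74.3% | 64.2% |

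With about one expected placebo responder in the last two rows, the normal approximation is rough. Read them as orders of size.

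**The case against.** The strongest reply is that the 3 days is an allowance for laboratory turnaround and not a planned screening length. The Schedule places Visit 1 nominally at Week -4. Exclusion criteria [24] and [25] require systemic non-biologic therapy and phototherapy to have stopped 28 days before baseline, and topical treatment 14 days before. Anyone still on such treatment at Visit 1 is screened for well over a week. HIV and hepatitis results also take time. This stands: very short screening is permitted, but nothing shows it to be planned or common. It does not close the gap, because patients already off treatment have no such delay, and TB tests and chest radiographs from the previous 3 months need not be repeated.

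A reader might infer that a definite share of the trial is lost, say 5% to 15% of 500, or 25 to 75 patients. The documents give neither the distribution of screening intervals nor diary adherence, so no such count is supported. With a lead time of 7 days or more and a same-day start, Step 2 puts the loss at about 3% (p = 0.8) or 0.3% (p = 0.9).

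A reader might also infer bias or an inflated type I error. Whether the baseline exists is settled before the first injection, so it should not depend on the assigned arm. The cost is precision and some representativeness.

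Finally, sites already have continuous access to the electronic outcome records (Protocol Appendix 3.2.1), so they can see diary completion before Visit 2. That helps, but no lead time or number of entries tells them what to look for.

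**Conclusion.** The point holds as a gap between two rules. A patient dosed 3 days after diary issue, or 4 days if entries start the next day, cannot have a PSS baseline. Below 7 days the baseline is possible but fragile.

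The certain part rests only on the documents' own rules. The availability percentages rest on assumed daily completion and independent days. That such a patient leaves the Week 16 PSS endpoint is an inference: the SAP does not say how a missing PSS baseline is counted, but a patient without one cannot be shown to meet the entry condition.

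The number affected cannot be derived. Power is hardly touched if the PSS effect is large (20% vs 2%), and falls noticeably only if response is low and the loss substantial. The primary endpoints and the other major secondary endpoints are unaffected. This is an inexpensive improvement, worth making because the missing data cannot be recovered later.

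**What to change.** In Protocol 5.1.1 and Schedule footnote b, state that Visit 2 is scheduled at least 7 days after the diary is issued, within the existing 28-day window. Count from diary issue, since Visit 1 procedures may be spread over several days. Say also that the first entry is made on the day of issue; otherwise a 7-day lead gives only 6 possible entries.

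Ask sites to review diary completion before Visit 2 as a prompt, and to use the remaining screening window where there is room. It should not be an eligibility gate. Section 6.4 limits rescreening to criteria [17] and [19], so a gate could exclude a patient from the whole trial, primary endpoints included, to protect one secondary endpoint. It would also select for patients who keep diaries well.

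A sentence in SAP 6.1.3 on how a missing PSS baseline is counted would settle the cases that remain.

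The cost is one protocol sentence and a site reminder. A patient who would have been dosed at day 3 waits 7 - 3 = 4 more days, and probably few patients are affected.

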- ⁿ Any enrolled patient who is HBcAb+ will undergo monitoring of HBV DNA with HBV DNA testing (see Section 9.4.5.4). Any patient with a positive HBV DNA test at any time must be discontinued from the study and receive appropriate follow-up medical care, including consideration for antiviral therapy.
- ^o Following screening, patients will not undergo monitoring for HCV RNA unless liver enzymes are elevated (see Section 9.4.5.5). Any patient with a positive HCV RNA test must be discontinued from the study and receive appropriate follow-up medical care, including consideration for antiviral therapy.
- ^p Immunogenicity samples should be collected prior to dosing on visits when mirikizumab is administered. A sample will be obtained at unscheduled visits if a patient develops an acute hypersensitivity event after administration of IP (see Section 7.8.2.1).
- ^q Scheduled PK samples are taken as an aliquot from the immunogenicity sample. Unscheduled PK samples, obtained if a patient develops an acute hypersensitivity event after administration of IP (see Section 7.8.2.1), will be collected in a separate tube.
- ^r FSH test is to be performed at screening for women who have had spontaneous amenorrhea for 6 to 12 months to confirm lack of childbearing potential.
- ^s If a patient discontinues IP early, the patient will complete the ETV and then enter the Post-Treatment Follow-up Period (V801 + V802).
- ^t All patients who receive IP but do not participate in Study AMAH must enter the Follow-up Period and complete V801 + V802.
- ^u Urinalysis assessed only for early termination due to an adverse event for which urinalysis is clinically indicated.

3. Introduction

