8.1. Discontinuation from Study Treatment

8.1.1. *Permanent Discontinuation from Study Treatment*

Patients for whom investigational product should be permanently discontinued, irrespective of the reason, should complete the Post-Treatment Follow-Up and then be permanently discontinued from the study. Section 8.2 provides the list of criteria for permanent discontinuation of patients from study treatment and the study.

Patients discontinuing from the investigational product prematurely for any reason should complete AE and other follow-up procedures per Section 2 (Schedule of Activities), Section 5.1.4 (Post-Treatment Follow-up Period), Section 9.2 (Adverse Events), and Section 9.4 (Safety) of this protocol.

8.1.2. *Temporary Interruption (Withholding) of Study Treatment*

Some possible reasons for temporarily withholding investigational product include, but are not limited to:

- Development of:
 - Serious or opportunistic infections, as described in Section 9.2.3).
 - Hypertension (see Section 9.4.2.1).
 - Latent TB infection (LTBI) (see Section 9.4.5.2).
 - Positive HBV DNA results that are below the level of quantification (see Section 9.4.5.4).
 - Hepatic event or liver test abnormality: Investigational product should be withheld and additional testing performed following consultation with the Lilly-designated medical monitor, if the results of repeat tests following elevated ALT, ALP or total bilirubin level (TBL) include one of the following (Section 9.4.6.1):
 - ALT ≥ 3 x ULN and TBL < 2 x ULN
 - ALP ≥ 2 x ULN and TBL < 2 x ULN
 - TBL ≥ 2 x ULN without increase from baseline in ALT/AST/ALP.
- Surgery: Patients requiring surgery at any time during the study should interrupt administration of the investigational product, beginning 8 weeks before the surgery or as early as possible within 8 weeks of surgery, and resume administration of the investigational product only after complete wound healing.

Cases that may merit temporary withholding of the study treatment should be discussed with the medical monitor. The medical monitor, in consultation with the investigator, will determine when it is appropriate to recommence study treatment.

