 - The patient develops a malignancy (Note: patients may be allowed to continue if they develop no more than 2 non-melanoma skin cancers during the study).
 - Any patient who has a change in disease phenotype at any time (for example, a change to pustular psoriasis).
 - If the patient remains at or above their baseline sPGA score at Week 16 (Visit 7) and Week 24 (Visit 9), or remains at or above their baseline PASI score at Week 16 (Visit 7) and Week 24 (Visit 9).
 - It is recommended that the patient be assessed by an appropriately trained professional to assist in deciding whether the patient is to be discontinued from study treatment and the study if:
 - i. The patient, at any time during the study, scores a 3 for Item 12 (Thoughts of Death or Suicide) on the 16-item Quick Inventory of Depressive Symptomatology (QIDS-SR16);

OR

- ii. Develops active suicidal ideation with some intent to act with or without a specific plan (“yes” to question 4 or 5 on the “Suicidal Ideation” portion of the C-SSRS);
OR
- iii. Develops suicide-related behaviors as recorded on the C-SSRS.
 - The patient develops active TB or HIV/AIDS during the study.
 - The patient becomes HBV DNA or HCV RNA positive. The patient should be referred to a specialist physician (see Sections 8.1.2 and 9.4.5.4 for HBV, and Section 9.4.5.5 for HCV).
- Patients will also be permanently discontinued from study drug, complete Post-Treatment Follow-up, and then permanently discontinued from the study in the following circumstances:
 - Enrollment in any other clinical study involving an investigational product or enrollment in any other type of medical research judged not to be scientifically or medically compatible with this study
 - Participation in the study needs to be stopped for medical, safety, regulatory, or other reasons consistent with applicable laws, regulations, and GCP
 - Investigator decision
 - The investigator decides that the patient should be discontinued from the study
 - If the patient, for any reason, requires treatment with another therapeutic agent that has been demonstrated to be effective for treatment of the study indication, discontinuation from the study occurs prior to introduction of the new agent

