9.4.5.4. Hepatitis B Screening

Patients who test HBsAg+, test HBcAb+ in conjunction with positive confirmatory HBV DNA test, or have positive HBV DNA test, regardless of HBsAb status, at screening will be excluded.

Any enrolled patient who is HBcAb+ will undergo periodic monitoring of HBV DNA as per the Schedule of Activities (Section 2).

In addition to the above, any enrolled patient who is HBcAb+ and who experiences an elevated ALT or AST level >3x ULN must undergo HBV DNA testing. If the HBV DNA test is negative, the investigator should consult with the Lilly-designated medical monitor regarding further management of the patient.

If the result of the HBV DNA test is positive but below quantification, study drug should be withheld and a repeat test done immediately. The Lilly-designated medical monitor should be contacted regarding study status of the patient. If the result of the HBV DNA test is positive and quantifiable, the patient must be discontinued from the study and should receive appropriate follow-up medical care, including consideration for antiviral therapy. A specialist physician in the care of patients with hepatitis (for example, infectious disease or hepatologist subspecialists) should be consulted, and the patient should potentially be started on antiviral therapy prior to discontinuation of any immunosuppressant therapy (including study drug). Timing of discontinuation from the study treatment, the study, and of any immunosuppressant therapy (including study drug) needs to be based on the recommendations of the consulting specialist physician in conjunction with the investigator and medical guidelines/standard of care.

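### Schedule of Activities footnote n requires study discontinuation for any positive HBV DNA test, while Sections 8.1.2 and 9.4.5.4 call for withholding and retesting when the result is below quantification

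*Protocol*

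**What the plan says.** Four places in the current protocol say what happens when an enrolled patient has a positive HBV DNA test.

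- **Section 2, Schedule of Activities, footnote n.** "Any patient with a positive HBV DNA test at any time must be discontinued from the study". The sentence names no level and makes no exception.
- **Section 9.4.5.4, Hepatitis B Screening.** For a low-level positive: "If the result of the HBV DNA test is positive but below quantification, study drug should be withheld and a repeat test done immediately". Then: "The Lilly-designated medical monitor should be contacted regarding study status of the patient". For the other kind: "If the result of the HBV DNA test is positive and quantifiable, the patient must be discontinued from the study". The timing of that discontinuation is to follow the advice of a consulting specialist together with the investigator.
- **Section 8.1.2, temporary interruption.** The listed reasons for temporarily withholding study drug include "Positive HBV DNA results that are below the level of quantification", with a reference to Section 9.4.5.4. The medical monitor, with the investigator, decides when treatment restarts.
- **Section 8.2, discontinuation from the study.** The list of criteria includes "The patient becomes HBV DNA or HCV RNA positive", with no threshold. The same bullet goes on to refer the reader to Sections 8.1.2 and 9.4.5.4 for HBV.

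The SAP has no rule on this point.

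**The concern.** A low-level positive in a monitored patient is an event the protocol expects and plans for. For that event, the table that directs visit procedures gives one instruction and the detailed safety section gives another. A site working from the Schedule of Activities would take the patient out of the study. A site working from Section 9.4.5.4 would withhold the dose, retest and leave study status open.

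Two things are at stake. The first is consistent handling of a safety signal across sites. The second is outcome data. A patient discontinued during induction goes to the early termination visit and then to follow-up (Section 5.1.2). Without a Week 16 assessment that patient is a non-responder under NRI (Protocol 10.3.1.1; SAP 6.3.1). A patient whose dose is withheld can attend Week 16, be assessed and, if a PASI 90 responder to mirikizumab, be re-randomized. The same contrast applies later for Week 52.

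**Working it through.** No arithmetic applies to the contradiction itself, so the check is a comparison of texts.

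**1. Is it current text?** Yes. Appendix 7 reprints footnote n without marked changes, while neighbouring footnotes f and g do carry edits. This is not a difference between superseded and current wording.

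**2. What does each place require?**

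| Place | Positive, below quantification | Positive, quantifiable |
|---|---|---|
| Footnote n | Discontinue from study (mandatory) | Discontinue from study (mandatory) |
| Section 9.4.5.4 | Withhold, repeat test at once, contact monitor on study status | Discontinue from study (mandatory), timing guided by specialist |
| Section 8.1.2 | Temporary withholding | Not listed |
| Section 8.2 | Discontinuation criterion without threshold, but refers to 8.1.2 and 9.4.5.4 | Discontinuation criterion |

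For quantifiable results the places agree that the patient leaves the study. For results below quantification, footnote n closes the question of study status, while Sections 9.4.5.4 and 8.1.2 leave it open pending a repeat test.

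**3. Does a cross-reference settle it?** Footnote n cites Section 9.4.5.4, but in its first sentence, which concerns monitoring of patients positive for hepatitis B core antibody (HBcAb). The discontinuation sentence that follows is separate and unqualified. No clause was found that says which section prevails. In Section 8.2 the reference sits in the same bullet as the criterion, so a reader is sent to the sections that make the distinction.

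**4. Can the case arise?** Exclusion criterion 13 removes patients with a positive HBV DNA test at screening, but HBcAb-positive patients with a negative HBV DNA test may enroll. The Schedule of Activities then tests them at Weeks 12, 24, 36 and 48, at early termination and in follow-up. Section 9.4.5.4 adds testing when ALT or AST exceeds 3 times the upper limit of normal.

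**5. Which endpoints can it touch?** Of the scheduled on-treatment tests, only Week 12 falls before the Week 16 primary endpoints and re-randomization. The Week 24, 36 and 48 tests fall before Week 52.

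**6. How many patients?** The documents give no expected number of HBcAb-positive enrollees and no rate of low-level positives. As a pure assumption, if 2% to 5% of 500 were HBcAb-positive, 0.02 × 500 = 10 to 0.05 × 500 = 25 patients would be monitored. That is the group tested, not the group affected.

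**The case against.** The best defence is that the outlier is one sentence in a table footnote. Sections 8.1.2 and 9.4.5.4 agree with each other, Section 8.2 points to both, and footnote n itself cites 9.4.5.4. A low-level positive also triggers contact with the medical monitor under 9.4.5.4, so a central party can bring sites into line. Much of this stands. It narrows the point to footnote n against two sections, and it means sites *may* diverge, not that they will. It does not remove the conflict, because a site that follows the footnote as written has no reason to ask about study status.

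The defence also corrects some stronger readings that a reader might infer:

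- *That Section 8.2 is a second flat contradiction.* Its own cross-references prevent that reading; it is only imprecise.
- *That one route leaves the patient on drug.* Both stop study drug at once, one by discontinuation and the other by withholding. They differ in study status and follow-up.
- *That a patient with withheld drug is certain to count as evaluable.* SAP 6.3.1 justifies NRI by a composite strategy in which a responder must also remain on assigned treatment. It does not say whether a temporary interruption meets that condition.

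**Conclusion.** The contradiction is real and confined to one situation: a post-enrollment HBV DNA result that is positive but below quantification. Footnote n on one side, and Sections 9.4.5.4 and 8.1.2 on the other, cannot both be followed for that result.

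Its size cannot be derived from the documents. The patients affected are those HBcAb-positive enrollees who later have such a result, a subset that is unknown and possibly very small. It would be wrong to read the assumed 10 to 25 monitored patients as exposed to the conflict, since all had to be HBV DNA negative at entry and some or all may stay so. Nor do the documents support a claim that power, type I error or the primary result would change. The case for correction rests on consistent safety handling and on a clear rule for whether such a patient remains in the study. No view is taken on which clinical rule is right.

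**What to change.** Reconcile footnote n with Sections 8.1.2 and 9.4.5.4, and clarify the HBV criterion in Section 8.2, so that every place states the same rule for results below quantification and the same rule for quantifiable results. Which rule applies to each is for the sponsor's medical team. The cost is protocol wording in the next amendment; no change to sample size or analysis method is needed.
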